3.1.3 Study intervention

- ξ Pulse oximetry embedded into CDSA
 - Pulse oximeters, with guidance (integrated into CDSA), training and mentorship
 - Tablet-based CDSAs, with guidance, training and mentorship
 - Refresher training on latest national / IMCI guidelines integrated with pulse oximetry and CDSA training
- ξ Pulse oximetry with paper job aid
 - Pulse oximeters, with guidance (pulse oximetry specific job-aid, plus adapted IMCI chart book), training and mentorship
 - Refresher training on latest national / IMCI guidelines integrated with pulse oximetry training
- ξ Control (routine care)
 - Refresher training on latest national / IMCI guidelines

3.1.4 Outcomes

This section provides an overview of the outcomes as listed in the protocol.

Primary outcomes

- ξ Proportion of children with a severe complication by Day 7
- ξ Proportion of children admitted to hospital within 24 hours of the Day 0 consultation and as a result of a referral (this is a proxy for 'appropriate referral' of children)

Secondary outcomes

- ξ Proportion of children with a severe complication by Day 28
- ξ Proportion of children cured at Day 7 follow-up
- ξ Proportion of children referred by a primary healthcare provider to a higher level of care at Day 0 consultation
- ξ Proportion of children who completed referral as reported at Day 7 follow-up

Other outcomes of interest – hypoxaemia (in intervention arms only)

- ξ Proportion of children with severe ($\text{SpO}_2 < 90\%$), moderate ($\text{SpO}_2 90 - 91\%$) and mild ($\text{SpO}_2 92 - 93\%$) hypoxaemia, adjusted for sites at high altitude
- ξ Proportion of children with hypoxaemia (according to differing cut-offs) with severe complication

- § Proportion of children with severe hypoxaemia not meeting any other clinical criteria for severe disease
- § Proportion of children referred with hypoxaemia who receive oxygen at hospital

Other outcomes of interest – referral and follow-up

- § Proportion of children with non-severe disease referred to a higher level of care on Day 0
- § Average length of stay (in days) of children admitted to hospital
- § Proportion of children attending scheduled follow-up at the same facility by Day 7
- § Proportion of children presenting for unscheduled follow-up to any health facility by Day 7

Other outcomes of interest – antimicrobial prescription

- § Proportion of children prescribed an antibiotic at Day 0
- § Proportion of children prescribed a diagnosis-appropriate antibiotic
- § Proportion of febrile children tested for malaria at Day 0
- § Proportion of malaria positive children prescribed an antimalarial
- § Proportion of malaria negative children prescribed an antimalarial
- § Proportion of untested children prescribed an antimalarial

Other factors for exploratory analyses

- § Additional socio-demographic characteristics, urban / rural location, distance from health facility, key household indicators such as maternal age and education
- § Main complaint / symptom categories (including cough / difficulty breathing, fever, diarrhoea and other) and time since onset of symptoms
- § Alternative hypoxaemia cut-offs
- § Health care provider severity classification
- § Facility and health system factors – type of facility, health care provider qualification and previous training

These exploratory analyses follow outside the scope of this statistical analysis plan and they will not be detailed further here but in a separate document.

3.2 Randomisation

The allocation sequence was generated separately for each country, stratified by facility type (dispensary/health center) and location (urban/rural) in Tanzania; by facility type (primary healthcare centres (HC)/community health centers) and district (Deoria, Sitapur, Unnao) in India. The target number of facilities were randomly selected from all eligible facilities and allocated to the trial arms. The remaining eligible facilities were retained in a back-up list for later allocation (using the same procedure) should the need arise (e.g. in case of facility exclusion at study start, or in case of need to add additional clusters in the event of recalculation of sample size). Given the cluster design, concealment will occur only at the stage of allocation of facilities, which will be conducted centrally and distributed to study sites. Participants will receive the intervention based on the facility they attend.

The allocation sequence generation was carried out by a statistician, independent from the study, prior to the recruitment of the first patient.

3.3 Blinding

This is an open-label study.

3.4 Sample Size

The sample size for the pragmatic RCT is calculated separately for each country, based on the following assumptions:

- ξ power of 80%
- ξ alpha level of 0.05 per arm
- ξ intra-cluster correlation coefficient (ICC) of 0.001
- ξ 1.1% severe complications in the control arm
- ξ 1.5% appropriate hospitalisations (within 24 hrs of Day 0 and as a results of referral) in the control arm

In India, initial sample size calculation for the three arm trial was based on having the power to detect a 30% or greater decrease in severe complication and 30% or greater increase in appropriate hospitalisation for each arm compared to control with 40 cluster per arm. This assumes average recruitment of 510 children per cluster over the 12 month period (total 40800), with an average of 110 per CHC per month and 20 children per PHC, assuming an average facility ratio CHC : PHC of 1:3. Following the decision, based on the pilot, not to introduce the CDSA, facilities were reallocated to the remaining two arms up to 60 facilities per arm.

In Tanzania, the study would have the power to detect a 30% or greater decrease in severe complication and a 30% or greater increase in appropriate hospitalisation for each arm compared to control with 22 clusters per arm. This assumes average recruitment of 1680 children per cluster over the 12 month period (total 110880), with an average of 350 children per health centre per month and 70 children per dispensary per month, assuming an average facility ratio health center : dispensary of 1:3.

3.5 Framework

TIMCI is a superiority study aiming to show the benefits, in terms of mortality and morbidity in children 0-59 months, of introducing pulse oximetry with updated IMCI chart booklet plus pulse oximetry job aid or pulse oximetry embedded into a CDSA, compared to routine care in primary health care facilities. The primary outcomes will be evaluated according to hierarchy of importance as described in Section 4.1.

3.6 Statistical interim Analysis and stopping Guidance

An interim analysis is planned to be conducted three months after the start of the study to assess recruitment rate, follow-up and sample size assumptions. The Data Monitoring Committee (DMC) will review the results and make recommendations to the Research Steering Committee (RSC) as to whether:

- ξ the sample size calculation should be adjusted based on estimated values in the control groups, as well as facility inclusion and recruitment;
- ξ the primary outcome measures should be revised due to a large percentage of missing values;
- ξ the study should be terminated prematurely due to inability to achieve its objectives.

A Data Monitoring Committee will be formed to monitor the progress of the trial. Further details are provided in the DMC charter [B]. Of note, no formal stopping rules are applied, and the criteria for the strength of evidence is left to the judgement of the DMC.

3.7 Timing for Analysis

An interim analysis will be triggered after three months from the study start. Data will be analysed after all children recruited in the first three months reach Day 7 follow-up and after data cleaning processes. The data export will include all data collected on these children up to the date of the export. Any interim analyses will be performed separately for Tanzania and India.

The final analysis will take place once all children have received a minimum of 28 days of follow-up. A pooled cross-country analysis will be conducted as well as individual country analyses.

3.8 Timing for Baseline and Outcome Assessments

Baseline is defined as the date of enrolment (Day 0) and time will be measured from this point.

Follow-up will occur 7 days and 28 days after Day 0. As defined in the protocol, no time window applies to Day 7 follow-up and a window of + 7 days applies to Day 28 follow-up. Refer to “Participants timeline” section of the protocol for more details.

The components (i.e. death and hospitalisation) required for the analysis of the primary outcomes will be assessed at both Day 7 and Day 28 follow-ups. For the main analysis, date of death and date of hospitalisation will be used irrespective of when these information are collected.

4 STATISTICAL PRINCIPLES

4.1 Confidence Intervals and p-Values

For the final analysis of the primary endpoints, a hierarchical fallback procedure will be used, which is a closed test procedure using a weighted Bonferroni [3, 4]. This method recycles unspent significant levels to test subsequent hypotheses with a pre-specified hypothesis sequence [5]. It uses alpha propagation making it more powerful than the Bonferroni method.

The primary outcomes will be evaluated according to hierarchy of importance as follows:

H_1 : There is no difference between the experimental arm and control arm with respect to severe complications by day 7.

H_2 : There is no difference between the experimental arm and control arm with respect to appropriate hospitalisation.

First, the null hypothesis H_{12} , which is that neither H_1 nor H_2 are significant, will be tested. The null hypothesis H_{12} will be rejected if either $p_1 \leq \alpha_1$ or $p_2 \leq \alpha_2$, where α is equally distributed between the endpoints i.e. $\alpha_1=0.025$ and $\alpha_2=0.025$.

Failure to reject the null hypothesis H_{12} we shall conclude the study to be negative as neither of the co-primary outcomes were significant and no further analysis will be performed. If the null hypothesis H_{12} is rejected, then H_1 and H_2 will be tested. If $p_2 \leq \alpha_2$ then we reject H_2 and test H_1 as $p_1 \leq \alpha$. If $p_2 > \alpha_2$ then we do not reject H_2 and test H_1 as $p_1 \leq \alpha_1$.

This procedure will be followed for each of the two experimental arms compared to the control arm. All outcomes will be evaluated regardless of the outcome of the first evaluation. For each intervention arm, the overall trial will be interpreted as positive if either primary outcome is positive compared to control.

Results estimates of primary and secondary outcomes will be presented along with the associated two-sided 95% confidence intervals, for both final analysis and analyses performed for DMC meetings. No adjustments will be made for the interim analysis and any other analysis carried out for the DMC review since they will not be conducted with the purpose of efficacy evaluation.

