8.3.1 Pragmatic cluster RCT

Analyses will follow CONSORT guidelines and intention-to-treat principles, including all participants as randomized. A flowchart will describe the inclusion and follow-up of participants by study arm.

Baseline characteristics will be described by study arm with summary statistics such as median and interquartile range or number and percentage; no formal testing between arms will be performed. Outcomes will be described by arm using summary statistics. The two primary outcomes, the proportion of children with a severe complication and the proportion of children appropriately hospitalized, will be assessed using a random effects logistic regression models with the cluster included as a random effect. Results will be reported with odds ratios, risk differences and 95% confidence intervals (CI). Binary secondary outcomes will be evaluated in the same way. Continuous secondary outcomes will be assessed using random effects linear regression models, reporting adjusted mean differences between arms with 95% CIs.

All models will be adjusted for randomization stratification factors and any baseline variables found to be randomly imbalanced across arms. Assessment for imbalances between baseline variables will be by visual inspection only; there will be no formal testing of baseline characteristics across randomized groups.^{53,54}

For the analysis of the primary endpoints, we will use a hierarchical fallback procedure, which is a closed test procedure using a weighted Bonferroni.^{55,56} This method recycles unspent significant levels to test subsequent hypotheses with a pre-specified hypothesis sequence.⁵⁷ This uses alpha propagation making it more powerful than the Bonferroni method.

The primary outcomes will be evaluated according to hierarchy of importance as follows:

H_1 : There is no difference between the experimental arm and control arm with respect to severe complications by day 7

H_2 : There is no difference between the experimental arm and control arm with respect to hospital admissions within 1 day of the primary consultation

First, we would test the null hypothesis H_{12} which is that neither H_1 nor H_2 are significant. We would reject the null hypothesis of H_{12} if either $p_1 \leq \alpha_1$ or $p_2 \leq \alpha_2$ where α is equally distributed between the endpoints i.e. $\alpha_1 = 0.025$ and $\alpha_2 = 0.025$.

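### The primary testing rule passes alpha only from appropriate hospitalisation (H2) to severe complications (H1): a valid rule, but unclear against the listed order, and it gives up power for H2 that could be had within the same error bound

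*SAP*

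**What the plan says.** SAP 4.1 says of the primary endpoints that "a hierarchical fallback procedure will be used, which is a closed test procedure using a weighted Bonferroni". On recycling, the same paragraph explains: "This method recycles unspent significant levels to test subsequent hypotheses with a pre-specified hypothesis sequence". The listing of the outcomes is introduced with "The primary outcomes will be evaluated according to hierarchy of importance as follows", and two null hypotheses come next:

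- H1, in first place: the experimental and control arms do not differ in severe complications by day 7.
- H2, in second place: "There is no difference between the experimental arm and control arm with respect to appropriate hospitalisation".

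The joint hypothesis H12 is tested first, with 0.025 for each endpoint. If it is rejected, the steps begin with H2. When p2 ≤ 0.025, "then we reject H_2 and test H_1 as" p1 ≤ α, that is, at 0.05. When p2 > 0.025, H2 is not rejected and H1 is tested at 0.025. That second branch puts no condition on p1.

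Protocol 8.3.1 has the same steps and says of the method: "This uses alpha propagation making it more powerful than the Bonferroni method". Both documents treat an intervention arm as positive if either primary outcome is positive against control.

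**The concern.** A reader who takes the listed order as the testing order expects a fallback that starts with H1 and hands its alpha to H2. The steps do the reverse, and neither document says that the testing order differs from the listing order or why. Two statisticians, one following the list and one following the steps, could report different confirmatory results from the same data.

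The one-way direction also means that H2 is never tested above 0.025, even after H1 has been rejected. The sample size (SAP 3.4, Protocol 6.6.1) assumes 80% power at alpha 0.05 for both outcomes. At stake is the confirmatory conclusion on appropriate hospitalisation, the outcome on which Protocol 6.4.2 expects the larger effect.

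**Working it through.** **1. What the steps amount to.** As written:

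- H1 is rejected if p1 ≤ 0.025, or if p2 ≤ 0.025 and p1 ≤ 0.05.
- H2 is rejected only if p2 ≤ 0.025.

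This is a closed test with H12 at 0.025/0.025, H1 alone at 0.05 and H2 alone at 0.025. Closure would allow H2 alone to be tested at 0.05 as well. Doing so gives Holm's procedure.

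**2. Where the verdicts differ.**

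| p1 | p2 | As written | Fallback, H1 first | Two-way (Holm) |
|---|---|---|---|---|
| 0.001 | 0.03 | H1 only | both | both |
| 0.03 | 0.001 | both | H2 only | both |

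**3. Reproducing the plan's power.** Inputs from SAP 3.4: ICC 0.001; severe complications 1.1% in control, 0.77% after a 30% decrease; appropriate hospitalisation 1.5%, 1.95% after a 30% increase; Tanzania 22 clusters of 1,680 per arm; India 40 clusters of 510 per arm at first, later up to 60. Two-sided tests are assumed, in line with the two-sided intervals in SAP 4.1.

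Design effect = 1 + (m − 1) × ICC, and n_eff = clusters × m / design effect:

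- Tanzania: 1 + 1,679 × 0.001 = 2.679; 36,960 / 2.679 = 13,796.
- India, 40: 1 + 509 × 0.001 = 1.509; 20,400 / 1.509 = 13,519.
- India, 60: 30,600 / 1.509 = 20,278.

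Power = Φ[(|difference| − z × SE_pooled) / SE_unpooled], without continuity correction. For H2 in Tanzania the difference is 0.0045, SE_pooled 0.0015677 and SE_unpooled 0.0015674.

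- At 0.05: (0.0045 − 1.960 × 0.0015677) / 0.0015674 = 0.911, so power is 0.819.
- At 0.025: (0.0045 − 2.2414 × 0.0015677) / 0.0015674 = 0.629, so power is 0.735.

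| Setting | H1 at 0.05 | H1 at 0.025 | H2 at 0.05 | H2 at 0.025 |
|---|---|---|---|---|
| Tanzania, 22 | 0.8127 | 0.7279 | 0.8188 | 0.7354 |
| India, 40 | 0.8049 | 0.7183 | 0.8110 | 0.7258 |
| India, 60 | 0.9323 | 0.8871 | 0.9358 | 0.8923 |

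The stated 80% at alpha 0.05 is reproduced to within 2 points for Tanzania and for India with 40 clusters.

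**4. Power for H2 under the two rules, independent tests assumed.** As written it is P(p2 ≤ 0.025). Two-way recycling adds P(p1 ≤ 0.025) × P(0.025 < p2 ≤ 0.05):

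- Tanzania: 0.7354 + 0.7279 × (0.8188 − 0.7354) = 0.796.
- India, 40: 0.7258 + 0.7183 × (0.8110 − 0.7258) = 0.787.
- India, 60: 0.8923 + 0.8871 × (0.9358 − 0.8923) = 0.931.

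Simulation with 4,000,000 pairs of test statistics per scenario agrees. The documents give no correlation between the two tests, so ±0.3 was tried. The gain for H2 is then 5.4 to 6.7 points in Tanzania and 3.5 to 4.2 points in India with 60 clusters.

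**5. Power for H1, independent tests.** It is the same under the written rule and two-way recycling: 0.790 in Tanzania and 0.928 in India (60). An H1-first fallback would lower it to 0.728 and 0.888.

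**6. Family-wise error per comparison with control (simulated, independent tests).**

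| Truth | As written | Two-way |
|---|---|---|
| Both nulls true | 0.049 | 0.049 |
| Only H1 false, very large effect | 0.025 | 0.050 |
| Only H2 false, very large effect | 0.050 | 0.050 |

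Neither rule exceeds 0.05 beyond simulation error, and correlations of ±0.3 do not change this.

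**The case against.** The strongest defence is that nothing is broken. A fallback is one-directional by design, and the documents name a fallback, not Holm. The steps are a proper closed weighted-Bonferroni fallback in the order H2 then H1. The claim of more power than Bonferroni is true of them: H1 in Tanzania goes from 0.728 to 0.790. Importance need not be testing order. Testing first the outcome with the larger expected effect (Protocol 6.4.2) and handing its alpha to the more important one is coherent. SAP 4.1 also reports all outcomes with 95% intervals, so the H2 result stays visible.

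Most of this stands. A reader might infer that the rule is not a closed test, or that the named procedure would reject H2 when p1 ≤ 0.025 and 0.025 < p2 ≤ 0.05. The documents do not support either. The rule is closed, and a fallback rejects H2 in that case only if its sequence starts with H1. Nor should a reader infer inflated error or a changed overall verdict: H12 is rejected in exactly the same cases under the written rule and under Holm.

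Two things remain. Neither document gives a reason for the direction, so the sequence is ambiguous. And if the intent was to favour H1, two-way recycling keeps all of that benefit and adds power for H2.

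**Conclusion.** The point holds as a matter of clarity and efficiency, not validity. Two-way recycling rejects everything that the written rule rejects, and more, within the same 0.05 bound per comparison. With independent tests the gain for H2 is about 6 points in Tanzania (0.735 to 0.796) and about 4 points in India at 60 clusters per arm (0.892 to 0.931), so one figure does not serve both countries. The result rests on the design rates, 30% effects, an ICC of 0.001 and the recruitment in SAP 3.4. Both outcomes draw on hospitalisations, so independence is only a working assumption, which is why the ±0.3 range is given. The error bound concerns the two outcomes within one arm-versus-control comparison; multiplicity across arms or countries is a separate matter.

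**What to change.** Before unblinded analysis, replace the last step in SAP 4.1 and Protocol 8.3.1 with two-way recycling (Holm): for each comparison with control, reject any primary outcome with p ≤ 0.025; if one is rejected, test the other at 0.05, whichever was rejected first. If one-way recycling is intended, state the testing order as H2 then H1 and give the reason.

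The edit is about two sentences in each document, with no new data and no change in sample size. It is not free. It alters the primary decision rule, so it needs a protocol amendment, and Protocol 10.2 sends important modifications to the ethics committees and registries. When H1 is false and H2 is true, the chance of falsely rejecting H2 rises from 0.025 to at most 0.05, still within the family-wise bound.

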4.2 Intervention adherence and Protocol Deviations

While in India pulse oximeter was indicated for all children, in Tanzania, pulse oximeter was indicated for all young infants and for older children with cough/difficult breathing or red/yellow IMCI classification. Cough/difficulty breathing and red/yellow IMCI classification are defined two ways, based on signs and symptoms as reported by the caregiver pre-consultation or on diagnosis made by the healthcare provider during the consultation. These definitions are detailed in a separate document and both will be used, separately, to assess intervention adherence.

Adherence will be evaluated separately for the two intervention arms on the basis of pulse oximeter and CDSA use when indicated.

- ξ Pulse oximetry adherence will be evaluated primarily using information on SpO₂ values from clinical records. Pulse oximetry will be considered used if the RA has found any SpO₂ recording (value readable or unreadable). Pulse oximetry will be considered not used if the RA did not find any recorded SpO₂. Adherence will be additionally evaluated based on pulse oximetry use as reported by the caregivers.
- ξ CDSA adherence will be evaluated by comparing the number of children enrolled and the number of children recorded into the CDSA database. These data will be used to explore further and in more details adherence to the CDSA, but outside the scope of this SAP and it will be detailed in a separate document.

Adherence will be reported overall and weekly by facility.

The following information will be summarised by arm to evaluate deviations to the study protocol:

- ξ Number and percentage of caregivers for which no Day 7 follow-up was attempted.
- ξ Number and percentage of caregivers for which no Day 28 follow-up was attempted.

More general deviations will be recorded by the study team in a study deviation log and categorised into minor and major.

4.3 Analysis Populations

All analyses will follow the intention to treat (ITT) principle, retaining facilities and participants in their initially randomised groups irrespective of the intervention received or any protocol violations. However, clusters provided from the start of the trial with a different intervention package than the one they were randomised to will be analysed according to the arm of the intervention they delivered.

A complete case set will also be defined, including only participants whose follow-up information are available (i.e. at least one follow-up was conducted). Analysis of the primary outcomes will be performed on both the ITT and the complete case set for final analysis and analyses for the DMC review.

No safety set will be defined but safety information will be reported overall and by use of intervention as defined in section 4.2.

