1 ADMINISTRATIVE INFORMATION

1.1 Document Scope

This document provides a detailed description of the methodologies that will be followed, as closely as possible, when analysing and reporting results from TIMCI RCT study. The planned analysis detailed in this document is in compliance with that briefly specified in the TIMCI RCT protocol, except if otherwise detailed.

The purpose of this Statistical Analysis Plan is to:

- ξ Ensure that the analysis is appropriate for the aims of the study, reflects good statistical practice in general, and minimises bias.
- ξ Ensure that the analyses performed are consistent with the conditions of the protocol.
- ξ Explain in detail how the data will be handled, covariates derived and analysed to ensure transparency and reproducibility, including enabling others to perform the actual analysis in the event of sickness or other absence.
- ξ Protect the project by helping it keep to timelines and within scope.

Additional exploratory or auxiliary analyses of data not specified in the protocol or this document are permitted but fall outside the scope of this Statistical Analysis Plan. Where analyses are presented which are not included in the SAP, these will be clearly indicated as such along with a justification as to their inclusion.

The analysis strategy will be made available if required by journals or referees when the main papers are submitted for publication. Additional analyses suggested by reviewers or editors will, if considered appropriate, be performed in accordance with the analysis plan, but if reported, the source of such post-hoc analyses shall be declared.

This document is written following the guidelines outlined in Gamble et al. [1]

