6.2.4 Pre-planned Sensitivity Analyses

Sensitivity analyses on the primary outcomes are planned and will be conducted:

- ξ On first encounters, which will include only the first enrolment episode of each child during the study period (as some children may attend the facility on more than one occasion). Separate presentations are identifiable from Day0 form as the caregiver is asked whether the child attended previously and within 28 days. This is the minimum number of days required for the disease episode to be considered a new one and not a repeat visit.
- ξ Looking at different hospitalisation appropriateness (based on different definitions of primary and secondary hospitalisations). Same day (Day0), 3 days and 7 days from Day0 will be used as cut-offs for different primary and secondary hospitalisation definitions.
- ξ Looking at different referral definitions:
 - ο A child will be considered to be referred if, at Day0, caregiver confirms that the child was urgently referred *and* the research assistant confirms that an urgent referral advice was recorded for the child².
 - ο A child will be considered to be referred if, at Day0, the research assistant confirms that an urgent referral advice was recorded for the child. If urgency is unknown, referral will be assumed to be urgent.

Additionally, a set of sensitivity analyses on the primary outcomes shall be carried out in case of substantial missing data (e.g. >10%) to evaluate the impact of each method on the primary outcomes results and take them into account when interpreting the final analysis results. Planned methods will include:

- ξ Worst case scenario
- ξ Complete cases
- ξ Multiple imputations with chained equations [11, 12]

Details of the methods are provided in Section 6.3.

Sensitivity analyses will only be performed for the final statistical analysis and not for interim analyses and DMC reports.

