6.3 Missing Data

Missing values will be primarily due to children lost to follow-up and not reached at Day 7 and Day 28.

The primary analysis will be performed assuming the best case scenario (alive and not hospitalised) for children lost to follow-up or withdrawn.

As described in Section 6.2.4, a set of sensitivity analysis will be performed in case of substantial missing data on the primary outcomes (e.g. >10%). Missing data will be treated as outline below:

- ξ Worst case scenario: children lost to follow-up or withdrawn will be assumed as dead or hospitalised.
- ξ Complete cases: children lost to follow-up or withdrawn will be excluded.
- ξ Multiple imputations with chained equations: under the assumption that children are lost to follow-up or withdrawn at random, chained equations with 50 imputed dataset, separately by treatment group, will be used. Relevant baseline characteristics and all available follow-up data will be used to impute death and hospitalisation (both primary and secondary) as binary variables.

Additionally, missing data will be described by arm and by relevant indicators, such as referral and severe disease to visually inspect for imbalances.

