6.4 Additional analyses

Primary outcomes will be further presented by adherence and indication groups (e.g. children for which pulse oximetry was indicated and was used, children for which pulse oximetry was indicated but was not used, etc.).

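### SAP 4.3 labels its primary set ITT but moves clusters given a different package from the start into the arm they delivered, and no as-randomised analysis is planned

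*SAP*

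**What the plan says.** Protocol 8.3.1 sets the rule without exception: "Analyses will follow CONSORT guidelines and intention-to-treat principles, including all participants as randomized".

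SAP 4.3 opens in the same way, "retaining facilities and participants in their initially randomised groups irrespective of the intervention received or any protocol violations". Its next sentence makes an exception for "clusters provided from the start of the trial with a different intervention package than the one they were randomised to": these "will be analysed according to the arm of the intervention they delivered". The resulting set is still called ITT. The only other set defined for the primary outcomes is a complete case set.

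SAP 1.1 says the planned analysis "is in compliance with that briefly specified in the TIMCI RCT protocol, except if otherwise detailed", so departures from the protocol are allowed if they are set out.

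On India, Protocol 6.6.1 and SAP 3.4 say that facilities were reallocated to the two remaining arms, up to 60 per arm, once the CDSA was not to be introduced. Neither says how.

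**The concern.** The two sentences of SAP 4.3 follow different principles. The first keeps a facility where randomisation put it, whatever it received. The second moves a whole facility according to what it received. The rule is not limited to chance delivery errors. A facility that got another package because of its staffing, patient volume or local preference would also be moved, and such features could be related to referral and admission, on which the primary outcomes depend. Any bias could go in either direction.

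At stake is what the primary result means. If a cluster qualifies, the estimate reported under the ITT label is partly an as-delivered estimate, and no planned analysis would show the reader the result that the protocol specified.

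**Working it through.** **1. Is there an as-randomised analysis anywhere?** Section by section:

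- SAP 4.3: the ITT set with the exception, and a complete case set. The complete case set is defined only by available follow-up; nothing returns a moved cluster to its randomised arm.
- SAP 6.2.4: under "Sensitivity analyses on the primary outcomes are planned and will be conducted" it lists first encounters, alternative hospitalisation cut-offs, alternative referral definitions and missing-data methods.
- SAP 6.3: "a set of sensitivity analysis will be performed in case of substantial missing data on the primary outcomes". This concerns missing data only.
- SAP 6.4: "Primary outcomes will be further presented by adherence and indication groups". This splits children by use and indication, not by randomised arm.
- SAP 6.5: deaths and secondary hospitalisations for safety.

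None gives the as-randomised result. SAP 4.2 reports adherence weekly by facility, which may help reveal a facility not using its package, and keeps a general deviation log. Neither is tied to this rule.

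**2. How much of an arm is one cluster?** Inputs from SAP 3.4 for Tanzania: 22 clusters per arm, 1,680 children per cluster on average, 350 per health centre per month, 70 per dispensary per month, ratio 1:3, 12 months.

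- Arm total: 22 × 1,680 = 36,960.
- Average cluster: 1,680 / 36,960 = 4.5%.
- Health centre: 350 × 12 = 4,200; 4,200 / 36,960 = 11.4%.
- Dispensary: 70 × 12 = 840; 840 / 36,960 = 2.3%.

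**3. Reproducing the planned Tanzanian sample size.** Inputs: ICC 0.001, severe complication 1.1% against 0.77%, power 80%, alpha 0.05 (taken as two-sided).

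- Design effect: 1 + (1,680 − 1) × 0.001 = 2.679.
- Individually randomised size (two proportions, pooled variance): 13,351 per arm.
- 13,351 × 2.679 = 35,768 (rounded up); 35,768 / 1,680 = 21.3, so 22 clusters. The plan's figure reproduces, with power 81.3%.

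**4. What as-randomised analysis would cost if clusters crossed over.** The documents give no count, so this is an illustration: k of 22 Tanzanian intervention clusters deliver control care from the start.

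- Effective size per arm: 36,960 / 2.679 = 13,796.
- Risk in the intervention arm as randomised: (1 − k/22) × 0.0077 + (k/22) × 0.011. The same form applies to hospitalisation, with 0.0195 and 0.015.
- Power: normal approximation, two-sided, equal cluster sizes, at the initial 0.025 level of SAP 4.1 and the 0.05 planning level of SAP 3.4.

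| k | Severe, 0.025 | Severe, 0.05 | Hospitalisation, 0.025 | Hospitalisation, 0.05 |
|---|---|---|---|---|
| 0 | 72.8% | 81.3% | 73.6% | 81.9% |
| 1 | 68.0% | 77.3% | 69.4% | 78.5% |
| 2 | 62.8% | 72.9% | 64.9% | 74.7% |
| 3 | 57.5% | 68.1% | 60.3% | 70.6% |

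Under SAP 4.1 only severe complication can be tested at 0.05, and only after the hospitalisation hypothesis is rejected.

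**5. Unequal cluster sizes.** The planned model has a random cluster effect (SAP 6.2.1), so a cluster of size m contributes about m / (1 + (m − 1) × 0.001).

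- 4,200 / 5.199 = 807.8 and 840 / 1.839 = 456.8.
- At 1:3: 22 × (0.25 × 807.8 + 0.75 × 456.8) ≈ 11,980 per arm.
- Severe-complication power at 0.025 for k = 0 to 3, counting each crossed cluster as 1/22 of the arm: about 66%, 61%, 56%, 51%.

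The level is lower but the fall is the same, about 15 points.

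**6. India, up to 60 clusters of 510 per arm.** Design effect 1 + 509 × 0.001 = 1.509; 60 × 510 = 30,600; 30,600 / 1.509 = 20,278. With 0 to 3 of 60 clusters crossed, severe-complication power at 0.025 is 88.7%, 87.5%, 86.1%, 84.7%.

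**The case against.** The best defence is that the exception is written down in advance, is narrow, and is of a kind that SAP 1.1 allows. It covers only whole clusters misassigned from the start; later non-adherence stays in the randomised arm. No affected cluster is documented. As-randomised analysis also dilutes the effect when clusters crossed over. All of this is true, and it limits the weight of the point. It does not supply a reason for the exception, justify the ITT label, or provide the missing companion analysis. Keeping the as-delivered estimate as a sensitivity analysis preserves what the exception was meant to offer.

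The power illustration covers one direction of crossover only, intervention clusters giving control care.

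A reader might infer from the India reallocation that many Indian facilities fall under the exception, or that the two-arm allocation there was not random. The documents support neither. The Protocol summary and section 5 describe the 1:1 allocation in India as random. Protocol 5.2 places the removal of the arm after the pilot and then describes a two-arm cluster randomised trial. SAP 3.2 says that an independent statistician generated the sequence, stratified by facility type and district, before the first patient was recruited. Nothing links the SAP 4.3 exception to the reallocated facilities. What remains is a gap in description: the reallocation step itself is not set out, and the reference in SAP 3.2 to reusing the same procedure concerns the back-up list.

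**Conclusion.** The point stands and should be fixed. SAP 4.3 departs from Protocol 8.3.1 without a stated reason, keeps the ITT label, and leaves no planned analysis that shows the as-randomised result.

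Its effect depends on a count that the documents do not give. If no cluster qualifies, the two analyses are identical. If any does, the loss falls on both primary outcomes, but only in comparisons that involve an arm the cluster leaves or joins. A reader might infer that the exception biases the trial by the share of children in a moved cluster. The documents give no basis for that: the shares show how much data would change arm, not the size or direction of any bias.

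The power figures rest on the planning rates, the planning ICC and an assumed number of crossovers. They measure what the fix could cost, not the harm done by the present rule.

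**What to change.** - **SAP 4.3.** Replace the exception with: *Every facility will be analysed in the arm of its final random allocation before the start of the definitive trial; the number, type, arm and reason for any facility given a different package from the start will be reported.* Naming the final allocation matters because any Indian facility first allocated to the dropped CDSA arm has no such arm in the two-arm trial.
- **SAP 6.2.4.** Add: *As-delivered analysis of the primary outcomes, with facilities given a different package from the start analysed by the package delivered.* Label it as a sensitivity analysis.
- **SAP 3.2, India.** State how facilities were reallocated after the CDSA arm was dropped and, if this was done at random, that the resulting allocation is the reference for analysis.

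The changes need no new data and no change in sample size. SAP 3.2 already describes allocation in the past tense, so the sponsor should be able to state the number of affected facilities now. The only statistical cost is the dilution shown above, and it arises only if clusters crossed over.
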